# Advanced Stage (Stage III, IV) ENKTL

Newly diagnosed patients with advanced stage disease will initially receive 2 cycles of single-agent pembrolizumab, 200mg IVPB every 3 weeks followed by reassessment by PET. Patients with no evidence of disease progression will receive another 2 cycles of pembrolizumab. In addition, patients with an "indeterminant response" by the LYRIC criteria (evidence of disease progression on PET but with clinical improvement) can be considered for another 2 cycles of pembrolizumab after discussion with the MSK PI. After 4 cycles of pembrolizumab, those who achieve a partial metabolic response (PMR) to pembrolizumab will proceed to 3 cycles of SMILE chemotherapy, involved site radiation therapy (if indicated and according to institutional standards), followed by 10 months maintenance therapy with pembrolizumab. Patients who do not achieve partial metabolic response to pembrolizumab will undergo biopsy. Those with biopsy showing persistent lymphoma will come off study and receive treatment per discretion of treating physician. If the biopsy shows pathologic complete response to therapy, patients will receive the same treatment as those with PMR.

(Refer to Stage III, IV Schema in Section 1.0 Protocol Summary)

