# 9.2 Stage III, IV ENKTL

Newly diagnosed patients with advanced stage disease will obtain baseline FDG-PET/CT simulation after a Radiation Oncology consultation. They will initially receive 2 cycles of single-agent pembrolizumab, 200mg IVPB every 3 weeks followed by reassessment by PET. Patients with no evidence of disease progression will receive another 2 cycles of pembrolizumab. In addition, patients with an "indeterminant response" by the LYRIC criteria (evidence of disease progression on PET but with clinical improvement) can be considered for another 2 cycles of pembrolizumab after discussion with the MSK PI. After 4 cycles of pembrolizumab, those who achieve a partial metabolic response (PMR) to pembrolizumab will proceed to 3 cycles of SMILE chemotherapy, up to 50.4 Gy of involved site radiation therapy (if determined to be appropriate by a Radiation Oncology Attending and according to institutional standards), followed by 10 months maintenance therapy with pembrolizumab. Patients who do not achieve partial metabolic response to pembrolizumab will undergo biopsy. Those with biopsy showing evidence of lymphoma will come off study and receive treatment per discretion of treating physician. If the biopsy shows no evidence of lymphoma, patients will receive the same treatment as those with PMR.

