#### 9.3 Pembrolizumab

# **Dosing**

Dosing of pembrolizumab is outlined in Table 3.0 below. Pembrolizumab will be administered every 3 weeks (21 days) (+/-3 days).

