# 10.0 EVALUATION DURING TREATMENT/INTERVENTION

# 10.1 Evaluations during treatment for stage I, II patients:

# Study Calendar, Stage I, II

Assessment Period	Screening 	Сус	le 1	Сус	le 2	ıf	Cycle 3	Сус	cle 4	In	Cycles 5	- Cycle 12	Post-Trea	atment
Study Days	Day -28 to 1	Day 1	Day 8-20	Day 1	Day 14- 21	PD	Day 1	Day 1	Day 14-21	volve		Day 14-21	End of Treatment	Follow up 
Visit Window 	-28 days	- 3 days		+/- 3 days		with n mothe	+/- 3 days	+/- 3 days	+/- 3 days	d Site				+/- 1 month
Informed consent	Х					no c erap				R				
Medical History	Х					< =				adi				
Review of concomitant medications		Х		Х		nical i and IS	Х	Х		ation	Х		Х	
Review of adverse events		Х		Х		l imp	Х	Х		Τh	Х		Х	
Physical Examination 		Х		Х		(Involved footnote	Х	Х		O O	Х		Х	Х
Vital Signs 		Х		Х		em lvo	Х	Х		rapy (ISF footnote	Х		Х	Х
ECOG/KPS		Х		Х		len lve	Х	Х		ot (E	Х		Х	Х
Hematology  and Chemistry 		Х		Х		t, proc d Site e 16]	Х	Х		7T)			Х	Х
HIV, Hepatitis B and Hepatitis C 	х					ᄁᅋ				OR SI				
Pregnancy test 8		Х				ed to 2 adiatio				 				
EBV PCR 9		Х		Х		2 c ion		Х		'n	Х		Х	Х
Referral to radiation oncology	х					ycles of Therapy				then				
FDG-PET/CT simulation 	Х					s of				ISR				
MRI nasal cavity (only for patients with nasal cavity disease)	х					SMILE y (see				T [see				
ECHO	Х													

ECG	Х											
Pulmonary function tests 11	Χ											
Baseline Biopsy or archive tissue 12	Х											
Research Tumor Biopsy 13			Х					X 				
PET/CT	X 				Х			Х		Cycle 8 & Cycle 12 	X	Х
Tumor assessment 14					Х			Х		Cycle 8 & Cycle 12		
cfDNA 		Х					Х		Х		Х	X 
Pembrolizumab 		Х		Х		Х	Х		Х			

- 1. Each cycle is 21 days in length.
- 2. **Screening assessments** must be completed prior to initiation of treatment. HIV, Hep B and C tests must be done within 6 months of start of treatment. Baseline biopsy must be done prior to treatment. All other assessments must be done within 28 days of treatment, except for laboratory tests which must be done within 14 days of treatment. Lab tests CBC and comp must be repeated within 3 days of C1D1. Pregnancy test is required for females of child-bearing potential and must be done within 7 days of initiating treatment.

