- 14. Tumor Assessment: is the response assessment after PET scans. Refer to Section 12.0 Criteria for Therapeutic Response/Outcome Assessment.
- 15. **Pembrolizumab**: Pembrolizumab is administered every 3 weeks (21 days) on Day 1 of each cycle, ± 3 days. Pembrolizumab is given 200m via IVPB infusion over 30 minutes (+/- 5 minutes).
- 16. **Reassessment by PET after 2 Cycles of pembrolizumab:** If there is no evidence of disease progression, participant will receive another 2 cycles of pembro. If evidence of disease progression on PET but with clinical improvement, participant can be considered for another 2 cycles of pembro after discussion with the study PI. Patients with progression of disease without evidence of clinical improvement will proceed to 2 cycles of SMILE chemotherapy and ISRT.
- 17. **Reassessment by PET after 4 Cycles of pembrolizumab**: If Complete Response (CR) by PET, patients will begin 45 Gy of involved site radiation (ISRT), and an additional 6 months (8 cycles) of maintenance pembrolizumab. ISRT will begin 2-6 weeks after Cycle 4 of pembrolizumab. Patients with less than CR will undergo a biopsy. If biopsy shows no evidence of lymphoma, patients will proceed with same treatment as those with PET CR. Patients with less than CR by PET and persistent evidence of disease on biopsy after 4 cycles of pembro will proceed to 2 cycles of SMILE chemotherapy and ISRT.
- 18. **Follow-up** includes: standard clinic visit and laboratory tests (CBC, comp only). EBV PCR every 3 months for 3 years. Imaging to be obtained every 6 months for 2 years post treatment. cfDNA to be collected 6 months, 1 year, and 2 years into follow up or until a new therapy is initiated.
- 19. PET/CT to be completed at baseline only if the patient will not be receiving radiation therapy.
- 20. Patients will be followed by PET/CT (skull apex to midthigh). If PET/CT is not feasible, patients may be followed with CT CAP plus CT nasal cavity (for patients with nasal cavity disease) after discussion with MSK PI. If followed by PET/CT, additional diagnostic CT is NOT required.
- 21. cfDNA to be collected at C1D1, C4D1, after SMILE or at C5D1 of pembrolizumab, end of treatment, and 6 months, 1 year, and 2 years into follow up or until a new therapy is initiated.

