- 15. **Pembrolizumab**: Pembrolizumab is administered every 3 weeks (21 days) on Day 1 of each cycle, ± 3 days. Pembrolizumab is given 200m via IVPB infusion over 30 minutes (+/- 5 minutes).
- 16. **Reassessment by PET after 4 Cycles of pembrolizumab**: If Partial Metabolic Response (PMR) by PET, patients may begin 45 Gy of involved site radiation (ISRT) if indicated, and an additional 6 months (8 cycles) of maintenance pembrolizumab. ISRT will begin 2-6 weeks after Cycle 4 of pembrolizumab. Patients with less than PMR will undergo a biopsy. If biopsy shows no evidence of lymphoma, patients will proceed with same treatment as those with PET CR. Patients with less than PMR by PET and persistent evidence of disease on biopsy after 4 cycles of pembro will be taken off study.
- 17. **Follow-up** includes: standard clinic visit and laboratory tests (CBC, comp only). EBV PCR every 3 months for 3 years. Imaging to be obtained every 6 months for 2 years post treatment. cfDNA to be collected 6 months, 1 year, and 2 years into follow up or until a new therapy is initiated.
- 18. PET/CT to be completed at baseline only if the patient will not be receiving radiation therapy.
- 19. Patients will be followed by PET/CT (skull apex to midthigh) If PET/CT is not feasible, patients may be followed with CT CAP plus CT nasal cavity (for patients with nasal cavity disease) after discussion with MSK PI. If followed by PET/CT, additional diagnostic CT is NOT required.
- 20. PET/CT to be done after last cycle of SMILE only may be done prior to treatment on C5D1. All other assessments marked should be done for every cycle of SMILE.
- 21. cfDNA to be collected at C1D1, C4D1, C5D1 of pembrolizumab, end of treatment, and 6 months, 1 year, and 2 years into follow up or until a new therapy is initiated.

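### Stage III/IV maintenance pembrolizumab has contradictory planned lengths: 8 cycles in calendar footnote 16, 12 cycles in the calendar grid, and 10 months in Sections 4.2 and 9.2

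*Combined protocol and SAP*

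**What the plan says.** Four places set out what a stage III/IV patient receives after cycle 4.

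- **Sections 4.2 and 9.2.** In Section 9.2, "those who achieve a partial metabolic response (PMR) to pembrolizumab will proceed to 3 cycles of SMILE chemotherapy", then radiation if appropriate, "followed by 10 months maintenance therapy with pembrolizumab". Section 4.2 gives the same sequence and the same length.
- **Section 10.2, calendar grid.** A SMILE block (cycles 1 to 3, with radiation if indicated) points to footnote 16. Pembrolizumab columns for cycles 5 to 16 follow. PET/CT and tumor assessment fall at cycles 8, 12 and 16.
- **Section 10.2, footnote 16.** After a partial metabolic response the patient may begin radiation ("ISRT) if indicated, and an additional 6 months (8 cycles) of maintenance pembrolizumab"). SMILE is not named. Radiation is to start 2 to 6 weeks after cycle 4. Footnote 20 of the same calendar does refer to SMILE: "PET/CT to be done after last cycle of SMILE only".
- **Section 9.5.** Advanced-stage radiation may be given between SMILE cycles or after SMILE.

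The dosing interval in Section 9.3 is: "Pembrolizumab will be administered every 3 weeks (21 days) (+/-3 days".

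For comparison, footnote 17 of the stage I/II calendar gives "an additional 6 months (8 cycles) of maintenance pembrolizumab". That grid runs from cycle 5 to cycle 12, with maintenance PET at "Cycle 8 & Cycle 12". There the footnote and the grid agree.

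**The concern.** A footnote and the calendar column that cites it should describe the same treatment. Here they differ in the number of maintenance cycles, and the treatment sections give a third figure in months. A site following footnote 16 would treat a patient as having finished after cycle 12. A site following the grid would plan four more doses and a further PET. The same patient, stopping after 12 doses, has completed treatment on one reading and stopped four cycles early on the other.

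That matters for the description of planned exposure, for any statement of how many patients completed treatment, and for which PET assessments count as on treatment. Section 14.0 analyses PFS and OS separately for advanced-stage patients, so the regimen behind those curves and the safety tables should be stated once.

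**Working it through.** **Inputs.** Footnote 16: 8 cycles, given as 6 months. Grid: cycles 5 to 16. Sections 4.2 and 9.2: 10 months. Cycle length: 21 days (Section 10.2, footnote 1). Initial phase: 4 cycles. One calendar month is taken as 30.44 days.

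**1. Footnote 16's own figure.** 8 × 21 = 168 days. This is 168/28 = 6.0 four-week months, or 168/30.44 = 5.5 calendar months. The footnote agrees with itself.

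**2. The grid.** 16 − 5 + 1 = 12 cycles, and 12 × 21 = 252 days = 8.3 calendar months. On the footnote's own scale (8 cycles = 6 months), 12 × 6/8 = 9.0 months.

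**3. The 10 months.** 10 × 30.44 = 304.4 days, and 304.4/21 = 14.5 cycles. On the footnote's scale, 10 × 8/6 = 13.3 cycles.

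| Source | Cycles | Months |
|---|---|---|
| Footnote 16 | 8 | 5.5 (stated as 6) |
| Grid | 12 | 8.3 to 9.0 |
| Sections 4.2 and 9.2 | 13.3 to 14.5 | 10 (as stated) |

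**4. Size of the firm conflict.** Total planned doses: 4 + 8 = 12 against 4 + 12 = 16. Shift in planned end of treatment: (12 − 8) × 21 = 84 days, or 12 weeks. Under footnote 16 the cycle 16 PET has no treatment cycle to attach to.

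**5. Does the visit window explain it?** If every visit were three days late (24 days), 8 cycles would last 192 days = 6.3 months and 12 cycles 288 days = 9.5 months. The window brings 12 cycles near 10 months but leaves 8 cycles far short. In any case 8 and 12 are counts, and no spacing turns one into the other.

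**6. Stage I/II comparison.** 12 − 5 + 1 = 8 cycles in the grid and 8 in footnote 17: no conflict.

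**7. Radiation timing.** SMILE is given every 21 to 28 days (Section 9.4), and the last drugs of a cycle fall between days 5 and 8 (Table 4). From the start of SMILE, the last drug of cycle 3 falls at 2 × 21 + 4 = 46 to 2 × 28 + 7 = 63 days. Footnote 16's upper limit is 6 × 7 = 42 days. Counted from the cycle 4 dose, radiation after all SMILE misses the limit even if SMILE began on the day of that dose. Counted from the end of cycle 4, the limit is 21 + 42 = 63 days after the dose, so it could be met only if SMILE began within 63 − 46 = 17 days of the dose. Radiation between SMILE cycles can fit: with SMILE started 21 days after the dose, cycle 1 drugs end on day 25 to 28 and cycle 2 starts on day 42 to 49, so a radiation start within days 14 to 42 is possible.

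**8. Patients affected.** Section 14.0 expects 66% early stage, so 0.34 × 19 = 6.5 advanced stage. The 8-cycle and 12-cycle readings part only at cycle 13, so only patients who reach the end of cycle 12 are affected. As an illustration, Section 3.0 reports 1 of 9 advanced-stage SMILE patients progression-free at 1 year. If SMILE began at week 12 and no radiation was given, cycle 5 would fall at week 21 to 24 and cycle 13 at week 45 to 48. At that historical rate, 6.5 × 1/9 = 0.7 patients would get there. The regimen differs, so this shows only that 6 to 7 is a ceiling.

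**The case against.** The strongest reply is that this is a drafting slip with little statistical effect. Much of that stands. The primary complete response rate is assessed after 4 cycles, N = 19 does not depend on maintenance, and PFS and OS are timed from treatment initiation. Several stronger readings do not stand:

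- *Follow-up and adverse event windows are undefined.* They are not. Sections 11.3 and 13.0 and the follow-up footnote count from each patient's actual last treatment or completion, so they move with it.
- *24 days is a maximum dosing interval, so 10 months is impossible.* Section 9.3 gives a visit window. The Administration text that follows it contemplates toxicity delays. The conflict rests on cycle counts, not on spacing.
- *Footnote 16 drops SMILE.* The footnote does not name SMILE, but its own column, footnote 20 and Sections 4.2 and 9.2 all do. The footnote is incomplete; it does not withdraw SMILE.
- *Biopsy-negative patients get a different treatment.* Footnote 16 refers them to the PET CR pathway and Section 9.2 to the PMR pathway. The available text does not show that the treatment differs.
- *Footnote 16 was carried over from stage I/II, so 8 cycles is the error.* The near-identical wording makes carry-over plausible, but the documents do not say so, and they do not show which length is intended.

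The grid's layout is broken in the available text. Even so, cycle 16 appears in the header and in both the PET and tumor assessment rows, so it is not a stray cell. The schema figure is not shown, but it could not remove a contradiction between printed passages, and the text gives no rule for which passage takes precedence.

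**Conclusion.** The inconsistency is real and limited. For stage III/IV patients who continue after cycle 4, 8 cycles cannot be squared with 12 cycles or with 10 months. The difference is 12 against 16 total planned doses and 84 days in the planned end of treatment, assuming 21-day cycles. The further gap between 12 cycles (8.3 to 9.5 months, depending on spacing and how a month is counted) and 10 months may be rounding, but it should be settled at the same time.

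Two points are secondary: SMILE is missing from footnote 16, and the footnote's radiation window conflicts with the Section 9.5 option of radiation after all SMILE. The second holds firmly only if the window is counted from the cycle 4 dose.

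What remains ambiguous is planned exposure, what counts as planned completion, and the on-treatment PET schedule for patients who reach the end of cycle 12. On the protocol's expected stage mix that is at most 6 to 7 patients and probably fewer. A reader might infer that the trial's main result is at risk; nothing in the documents supports that.

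**What to change.** Reconcile Sections 4.2, 9.2 and 9.5 with the Section 10.2 calendar and its footnote 16, so that each gives the same maintenance length, stated in cycles, the same order of SMILE, radiation and maintenance, and the same radiation start. For that start, say whether it is counted from the cycle 4 dose or from the end of cycle 4. Name SMILE in footnote 16 if the intended sequence includes it. Match the calendar columns and the PET and tumor assessment time points to the chosen length, and check that the Section 1.0 schema agrees. The sponsor decides which length, sequence and timing are intended; this review takes no view.

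The cost is a text amendment. The sample size and the primary analysis do not change.

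### Stage III–IV calendar footnote 16 carries over early-stage text: it omits the three SMILE cycles and conflicts with Sections 4.2, 9.2 and 9.5 and with its own table

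*Combined protocol and SAP*

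**What the plan says.** **Body text, stage III–IV, after four cycles of pembrolizumab.** Section 4.2 says that patients with PMR "will proceed to 3 cycles of SMILE chemotherapy, involved site radiation therapy (if indicated and according to institutional standards"), followed by 10 months of maintenance. Section 9.2 says that they "will proceed to 3 cycles of SMILE chemotherapy, up to 50.4 Gy of involved site radiation therapy", again with 10 months of maintenance to follow. Under Section 9.2 a patient below PMR whose biopsy shows no lymphoma is treated like a patient with PMR. Section 9.5 lets advanced-stage ISRT fall between SMILE cycles or after SMILE.

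**Footnote 16 of the stage III–IV calendar (Section 10.2), same patients, same decision.** With PMR, "patients may begin 45 Gy of involved site radiation (ISRT) if indicated, and an additional 6 months (8 cycles) of maintenance pembrolizumab". On timing: "ISRT will begin 2-6 weeks after Cycle 4 of pembrolizumab. Patients with less than PMR will undergo a biopsy". After a negative biopsy, "patients will proceed with same treatment as those with PET CR. Patients with less than PMR by PET" is how the text runs on. SMILE does not appear in the footnote.

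**The table that the footnote annotates.** As far as the broken extraction can be pieced together, the column that cites footnote 16 is headed SMILE cycles 1 to 3 with ISRT if indicated. A further column holds assessments after each SMILE cycle. Footnote 20 reads "PET/CT to be done after last cycle of SMILE only may be done prior to treatment on C5D1".

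**Footnote 17 of the stage I–II calendar (Section 10.1).** It has the same timing sentence, "ISRT will begin 2-6 weeks after Cycle 4 of pembrolizumab. Patients with less than CR will undergo a biopsy", and the same biopsy sentence, "If biopsy shows no evidence of lymphoma, patients will proceed with same treatment as those with PET CR". It also has the same 45 Gy and the same 6 months (8 cycles) of maintenance.

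**The concern.** The footnote is an operative instruction at the point where stage III–IV treatment is decided, and the calendar column sends the reader to it. Taken alone, it takes a patient with PMR from pembrolizumab to radiation and maintenance with no chemotherapy, or to radiation before chemotherapy. It also shortens maintenance and drops the higher radiation dose. For a biopsy-negative patient it points to a PET-CR path that the footnote does not define and that the text of Sections 4.2 and 9.2 does not describe for advanced stage.

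The trial runs at the coordinating centre and an external institution, and the protocol states no rule on which text prevails. If sites read it differently, advanced-stage patients would receive different regimens under one label. Section 14 reports PFS and OS separately for this group, and with so few patients one or two treated differently could change those curves.

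**Working it through.** The plan gives no figure for this point. Its one design figure, the interval 0.18–0.62 for a 40% CR rate with n = 19, reproduces as 0.40 ± 1.96 × √(0.40 × 0.60 / 19) = 0.40 ± 0.22 and plays no part here. The check is a comparison of texts plus timing arithmetic.

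**1. Side by side (stage III–IV, after cycle 4)**

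| Item | Sections 4.2, 9.2, 9.5 | Footnote 16 | Early-stage footnote 17 |
|---|---|---|---|
| SMILE after PMR | 3 cycles | not mentioned | not applicable (CR goes straight to ISRT) |
| ISRT start | between SMILE cycles or after SMILE | 2–6 weeks after cycle 4 | 2–6 weeks after cycle 4 |
| ISRT dose | up to 50.4 Gy | 45 Gy | 45 Gy |
| Negative biopsy | treated as PMR | treated as PET CR | treated as PET CR |
| Maintenance | 10 months | 6 months (8 cycles) | 6 months (8 cycles) |

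Wherever footnote 16 departs from the advanced-stage text, it agrees with the early-stage CR path. It does use the advanced-stage PMR threshold and the off-study rule for persistent disease. That is the pattern of a copied footnote only partly adapted.

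**2. Can ISRT follow three SMILE cycles within 6 weeks?**

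Inputs: PET on cycle-4 day 14–21, ±3 days (calendar); SMILE every 21–28 days (Section 9.4); last SMILE drugs on day 5–8 (Table 4). Assumption: SMILE starts on the day of the PET. Section 9.4 leaves the start to the physician, and a later start moves every date later.

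Count days from the cycle-4 dose (day 0), with s = SMILE start and L = interval.

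- s runs from 13 − 3 = 10 to 20 + 3 = 23.
- Day 1 of SMILE 3 = s + 2L: 10 + 42 = 52 to 23 + 56 = 79.
- End of the third cycle = s + 3L: 10 + 63 = 73 to 23 + 84 = 107.
- Six-week limit from the dose: day 42. No schedule reaches even the start of SMILE 3 by then.
- Extreme bound, with SMILE starting on the cycle-4 dose day itself: the last SMILE 3 drug falls on 0 + 42 + 4 = day 46, still past 42.
- If the six weeks run from the end of cycle 4, the limit is 21 + 42 = day 63. A full third cycle (day 73 at the earliest) still misses it. The fastest schedules finish the SMILE 3 drugs on 10 + 42 + 4 = day 56, so only a start immediately after those drugs could fit.

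**3. Can ISRT between SMILE cycles fit the 2–6 week window (day 14–42)?**

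- The last SMILE 1 drug falls on day 10 + 4 = 14 to 23 + 7 = 30, inside the window.
- The full first cycle ends on s + L: 10 + 21 = 31 to 23 + 28 = 51, partly inside.

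So the timing conflict with Section 9.5 is partial.

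**4. Maintenance length (month = 30.4375 days)**

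- Footnote 16: 8 × 3 = 24 weeks, about 5.5 months.
- Calendar cycles 5–16: 12 × 3 = 36 weeks, about 8.3 months.
- Sections 4.2 and 9.2: 10 months, about 43.5 weeks or 14.5 cycles.

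These are three different durations.

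**5. How many patients?** Section 14 expects 66% early stage, so (1 − 0.66) × 19 = 6.5 advanced-stage patients. Only those with PMR or a negative biopsy reach this step, and ISRT timing matters only for those with an ISRT indication.

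**The case against.** The best defence is that no careful site would go wrong. Section 9 is the treatment plan and Section 10 covers evaluations. SMILE is stated in Sections 4.2 and 9.2, in the column that leads to footnote 16, in the post-SMILE assessment column and in footnote 20. The footnote itself is permissive about starting ISRT. This stands as a reason to keep the concern modest, but it does not remove it. The permissive wording does not restore SMILE, the timing sentence that follows is not permissive, and no precedence rule settles the conflict.

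The dose difference is also softer than it looks: 45 Gy lies within a ceiling of 50.4 Gy. The loss is the option of the higher dose, which Section 5.3.2 allows for patients short of CR.

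Four stronger readings are tempting and not supported:

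- A reader might infer that the 2–6 week window can never be met in advanced stage. Section 9.5 allows ISRT between SMILE cycles, and such a start can fall inside it.
- A reader might infer that stage III–IV complete responders have no treatment path. Sections 4.2 and 9.2 name only PMR, but the schema figure is not shown, and PMR may be meant as a minimum.
- A reader might infer that patients were treated without SMILE. The documents contain no delivery data.
- A reader might infer that the CR rate is compromised. That response is assessed before this step.

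**Conclusion.** Footnote 16 is wrong as written and should be corrected. It omits three chemotherapy cycles, sets an ISRT window that cannot be met if ISRT follows three full SMILE cycles, refers biopsy-negative patients to the wrong comparator group, and carries the early-stage maintenance length and radiation dose.

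The weight is moderate to low. It touches a subset of about 6–7 expected patients, and the correct regimen is stated elsewhere several times. The possible consequences are for those patients' treatment and safety and for the descriptive advanced-stage PFS and OS. These are possibilities, not shown effects. The primary CR rate, the sample size and the planned analyses are unaffected.

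The textual conflict needs no assumption. The timing result assumes that SMILE does not start before the cycle-4 PET and runs at 21–28 day intervals. It holds whether the six weeks are counted from the cycle-4 dose or from the end of cycle 4, provided the third SMILE cycle is completed.

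**What to change.** Rewrite footnote 16 to match Sections 9.2 and 9.5:

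- PMR by PET, or a biopsy with no evidence of lymphoma, leads to 3 cycles of SMILE.
- ISRT, if indicated, is given up to 50.4 Gy, between SMILE cycles or after SMILE.
- Maintenance pembrolizumab follows for 10 months. Reconcile this with calendar cycles 5–16, which are only 12 three-week cycles.
- Delete the 2–6 week sentence, and refer biopsy-negative patients to the PMR path instead of PET CR.

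The investigators should confirm that stage III–IV complete responders follow the same path as PMR; that is a clinical decision and should be written down.

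As an optional clarification, state in Section 9.5 that the 2–6 week rule applies to stage I–II patients who go directly to ISRT. Section 9.1 sends other early-stage patients to two SMILE cycles first, and those who progress after cycle 2 have no cycle 4 to count from. Footnote 17 needs no change, because its timing sentence already follows PET CR.

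The cost is a small protocol amendment: one footnote, a decision on the number of maintenance cycles and, if wanted, one qualifier. Sample size and analysis do not change.

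### Footnote 16 of the stage III–IV calendar disagrees with Sections 4.2 and 9.2 on treatment after Cycle 4: it gives 8 maintenance cycles instead of 10 months, does not name SMILE, and describes the negative-biopsy branch ambiguously

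*Combined protocol and SAP*

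**What the plan says.** **Treatment plan.** For stage III–IV patients after four cycles of pembrolizumab, Section 9.2 states that "those who achieve a partial metabolic response (PMR) to pembrolizumab will proceed to 3 cycles of SMILE chemotherapy", then "up to 50.4 Gy of involved site radiation therapy" where a radiation oncologist judges it appropriate, "followed by 10 months maintenance therapy with pembrolizumab". Section 4.2 gives the same sequence without a radiation dose. For less than PMR with a negative biopsy, Section 9.2 says "If the biopsy shows no evidence of lymphoma, patients will receive the same treatment as those with PMR" and Section 4.2 says "If the biopsy shows pathologic complete response to therapy, patients will receive the same treatment as those with PMR".

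**Footnote 16 of the stage III–IV calendar (Section 10.2).** On radiation, its PMR sentence reads "If Partial Metabolic Response (PMR) by PET, patients may begin 45 Gy of involved site radiation (ISRT) if indicated". On maintenance, the same sentence reads "and an additional 6 months (8 cycles) of maintenance pembrolizumab". The footnote has radiation start two to six weeks after Cycle 4. For less than PMR and a negative biopsy: "If biopsy shows no evidence of lymphoma, patients will proceed with same treatment as those with PET CR".

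**Calendar grid (Section 10.2).** The column that cites footnote 16 is labelled with SMILE cycles 1–3 and ISRT if indicated. Maintenance runs under a header of Cycles 5–16. Footnote 20 places a PET/CT after the last SMILE cycle, before Cycle 5.

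**Section 9.5.** Advanced-stage ISRT may be given between SMILE cycles or once SMILE is complete.

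**The concern.** The calendar sends its users to footnote 16 for the decision after Cycle 4, so the footnote works as a treatment rule. Its PMR sentence covers every advanced-stage patient with PMR, not a rare branch. The trial is multicenter: about 10 of 19 patients come from the lead center, which leaves about 9 to be treated elsewhere by staff who rely on the written text.

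A site that follows the footnote would stop maintenance well before one that follows Section 9.2. Section 14.0 analyses PFS and OS separately for advanced stage, so a few patients treated under different rules would mix regimens within a very small group.

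The probable cause is text carried over from stage I–II footnote 17. The negative-biopsy sentence and the ISRT-timing sentence are the same in both footnotes, and 45 Gy and 6 months (8 cycles) match as well. That is an inference, though a well-supported one.

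**Working it through.** **Side by side**

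| Item | Sections 4.2 and 9.2 | Footnote 16 | Stage III–IV calendar grid |
|---|---|---|---|
| SMILE after PMR | 3 cycles | not named | column for SMILE cycles 1–3 |
| Maintenance | 10 months | 6 months (8 cycles) | Cycles 5–16 |
| Less than PMR, negative biopsy | as for PMR | as for PET CR | – |
| ISRT start | Section 9.5: between SMILE cycles or after them | 2–6 weeks after Cycle 4 | – |
| ISRT dose | 9.2: up to 50.4 Gy; 4.2: none given | 45 Gy | – |

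**Maintenance length.** Inputs: a 21-day cycle (Section 10.2, footnote 1) and a month of 365.25/12 = 30.44 days.
- Footnote 16: 8 × 21 = 168 days = 24 weeks; 168/30.44 = 5.5 months. The footnote's own equation of 6 months with 8 cycles is reproduced, with rounding.
- Calendar header: Cycles 5 to 16 are 16 − 5 + 1 = 12 cycles; 12 × 21 = 252 days = 36 weeks = 8.3 months.
- Sections 4.2 and 9.2: 10 × 30.44 = 304 days, about 43 weeks; 304.4/21 = 14.5, so 14–15 cycles.

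These are three different lengths. Against the footnote, the header adds 12 − 8 = 4 doses and 10 months adds 6–7. Eight cycles fit the stage I–II calendar (Cycles 5–12) but not the stage III–IV calendar, which schedules a PET/CT at Cycle 16.

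**Negative biopsy.** The available stage III–IV text has no separate PET CR branch. A treatment after PET CR is written out only for stage I–II (Sections 4.2 and 9.1, and footnote 17), and it contains no SMILE. Sections 4.2, 9.2 and footnote 16 all divide stage III–IV patients into PMR and less than PMR. A patient in PET CR is not below PMR and most naturally falls on the PMR side. The footnote can therefore be read as agreeing with Section 9.2 or as pointing to the stage I–II regimen.

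**ISRT timing.** Inputs: Cycle 4 PET on day 14–21 (calendar) and SMILE every 21–28 days (Section 9.4). Assume SMILE starts on day 14 of Cycle 4, which is 13 days after Cycle 4 Day 1 and 7 days before the cycle ends, with 21-day SMILE cycles.
- After three SMILE cycles: 13 + 63 = 76 days = 10.9 weeks from Cycle 4 Day 1, or −7 + 63 = 56 days = 8.0 weeks from the end of Cycle 4. Both lie outside 2–6 weeks.
- After one SMILE cycle: 13 + 21 = 34 days = 4.9 weeks, or −7 + 21 = 14 days = 2 weeks. Both lie inside.

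The footnote therefore excludes one of the two options in Section 9.5 and leaves the other open.

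**Dose.** At 1.8 Gy per fraction, 45/1.8 = 25 and 50.4/1.8 = 28 fractions, as Section 5.3.2 states. 45 Gy lies within Section 9.2's ceiling, and Section 5.3.2 makes the increase optional for less than CR.

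**Patients concerned.** Section 14.0 expects 66% early stage, so 0.34 × 19 = 6.46, or 6–7 advanced-stage patients. One patient is 1/6.46 = 15% of that group.

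**The case against.** The strongest reply is that a reader of the whole protocol would not go wrong. Sections 4.2 and 9.2 agree with each other. The column that leads to footnote 16 names SMILE cycles 1–3, the next column covers visits after those cycles, and footnote 20 schedules a scan after the last one. Section 12.0 counts a negative biopsy as CR, which may explain the PET CR wording. The stage III–IV schema is a figure not available here and could define a CR branch.

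Much of this stands, and it rules out several stronger readings:
- A reader might infer that PMR patients would miss SMILE. The footnote's silence creates that risk, but the grid and footnote 20 make it unlikely.
- A reader might infer that biopsy-negative patients are assigned the SMILE-free stage I–II regimen. The documents do not say so; PET CR may simply mean PMR or better.
- A reader might see 45 Gy against 50.4 Gy as a contradiction. The lower dose is permitted by the higher limit.
- A reader might call the ISRT window incompatible with Section 9.5. It is only narrower.

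The reply does not reach the maintenance length. Eight cycles, 12 cycles and 10 months cannot all hold, and nothing in the available text says which governs. Nor does it explain why the footnote that the calendar cites leaves out a component that Sections 4.2 and 9.2 require.

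**Conclusion.** The point holds in a limited form. The firm conflict is maintenance: 24 weeks in the footnote, 36 weeks in the calendar header, about 43 weeks in Sections 4.2 and 9.2. The missing mention of SMILE makes the footnote incomplete, the negative-biopsy sentence is ambiguous, and the ISRT window is too narrow for radiation after all three SMILE cycles.

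The figure of 6–7 patients rests on the planned stage mix and is reached only if all of them get to the Cycle 4 PET. The documents give no rate for PMR or for less than PMR with a negative biopsy, so neither subgroup can be sized.

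The effect is on later treatment, safety, and the descriptive advanced-stage PFS and OS. The primary CR rate is unaffected: response is judged after four cycles, before the texts diverge, and a negative biopsy counts as CR under Sections 12.0 and 14.0 either way. The sample size is also unaffected. This should be corrected, but it does not put the trial's main result in doubt.

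**What to change.** Reword footnote 16 so that stage III–IV patients with PMR or better, and those with less than PMR but a negative biopsy, receive the Section 9.2 treatment: three cycles of SMILE, ISRT if appropriate with the timing of Section 9.5, then maintenance. Delete the 6 months (8 cycles) and the two-to-six-week ISRT start from that footnote.

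State one number of maintenance cycles, identically in Section 4.2, Section 9.2, footnote 16 and the calendar header. Choosing between 12 and 14–15 cycles is a clinical decision for the sponsor, not an editorial one.

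If advanced-stage patients have already been treated, record which rule each followed, so that the PFS and OS description can say so.

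The cost is one reworded footnote and one decision on cycle number. The primary endpoint, sample size and analysis stay as they are.
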